#### **WP2:8.4 Subgroup analyses**

There are no a priori planned sub-group analyses. However, it is anticipated that the estimated graphical Markov model in WP2 will be used to assess competing hypotheses during the development of the intervention in WP4.

#### **WP2:8.5 Adjusted analysis**

The proposed models will examine the association between any two (or more) variables partitioning out the contribution of different groups of variables as relevant, led by group discussions (WP4). The rates of transitions from the multistate models will be adjusted for age and sex and include important centre-and patient-level explanatory variables.

#### **WP2:8.7 Subject population**

All English renal units and all patients commencing renal replacement therapy in them.

#### **WP2:8.8 Procedure(s) to account for missing or spurious data**

The survey will be conducted in a manner to minimise the possibility of missing data related to centre practices, with redundancy in the questions posed to different members of the team with different roles in the renal unit. The Renal Registry is characterised by high levels of data completeness, except for comorbidity data as the returns to the Registry from different units are variable. Patterns and levels of missigness will be explored. Maximum likelihood estimation will be used to fit all the models, as this method of estimation yields parameter estimates that are not affected by the exclusion of missing outcome data if a missing-at-random assumption is plausible. Depending on the amount of missing data, expectation-maximisation (EM) imputation will be considered because it preserves the covariance structure of the data, combined with multiple imputation to adjust the estimated standard errors, and thus obtain estimates that make effective use of all the available data.

#### **WP2:9 DATA HANDLING**

The Online Survey tool assigns each participant a unique identifying number, and does not record any personal information, cookies, IP addresses or email addresses. Participants will

not be asked to provide any personal information apart from some sociodemographic data (age, gender, ethnic group), and some brief information about their job (role, time in post). This information will be non-identifiable. If any participants disclose personal information via free text survey response options, these will be removed by the research team at the point of exporting survey responses from the Online Survey database to the database that will be kept securely at University of Birmingham for the purposes of analysis.

If respondents have provided any contact details to claim the £25 reimbursement being offered, these details will be removed from the database before analysis.

### ***WP2:9.3 Access to data***

Only members of the research team will have access to the anonymised survey data.

### ***WP2:9.4 Data sharing agreements***

Keele University will execute the applicable data sharing agreements to enable transfer of study data between collaborating organisations, storage and analysis of data as applicable. These data sharing agreements will include the detail on compliance with the data protection laws as relevant, data controller obligations, data protection particulars with regards to processing and information security arrangements.

### ***WP2:9.5 Survey Data Archiving (before and after linkage to UK Registry Data)***

Survey data will be collected in Birmingham and then passed to Keele for linkage to the UK Registry Data. The primary survey data will be archived under the University of Birmingham's regulations on the retention of research data, anonymised, analysed data will be retained for ten years, and will be securely archived on University of Birmingham premises, with the local PI as data custodian.

At Keele University, archiving will be completed as soon as possible after study closure, analysis and dissemination and will be in accordance with Keele University Archiving Standard Operating Procedure. At the end of the study, data will be securely archived in line with the Sponsor's procedures for 10 years after 'End of Study Declaration' (date of end of study submission to Regulatory bodies) and until the sponsor authorises destruction.

## **WORK PACKAGE 3 (WP3): HEALTH ECONOMICS**

### **WP3:8 ANALYSIS PLAN**

The first step in the economic will be to review existing models of UK dialysis services, particularly those submitted for NICE assessment. The purpose of this review will be to inform the conceptualisation of the model including which events to include and the model structure e.g. to use a time to event based model or a state transition model. We will seek feedback on proposed model structures from stakeholders.

After the conceptualisation is near finalised we will undertake a review of parameter values used in existing models to ensure the model is based on the most up to date sources. We will search for estimates of the cost of treatments and the health-related quality of life (HRQoL) associated with dialysis modalities and complications that require hospitalisation. Unit costs will be based on national NHS reference costs and drug prices will be taken from British National Formulary. HRQoL values will be retrieved from the literature or from existing datasets (SHAREHD & UKCath/DOPPS). Regression analysis in UKRR and other data sources for the purpose of quantifying rate of transitions between states or the time until a dialysis event occurs. Minor adjustments to the model structure may take place based on the availability of data in existing datasets.

Once all parameter values have been retrieved we will build the economic model in the software package R. To check the validity of the model we will compare its outputs to those from existing registries and modelling studies and share results at an early stage with stakeholders. Model calibration will take place if there is not a close fit to existing sources, and this would involve adjusting the parameter values of uncertain model inputs to ensure the model outcomes closely reflects findings from registry data. There will be sensitivity testing of parameter inputs to examine which model assumptions and parameter values are the main drivers of the economic outcomes.

## **WP3:9 DATA HANDLING**

### ***WP3:9.1 Data collection tools and source document identification***

The UK renal registry data is extracted from the renal computer systems at individual renal centres, and securely transferred to the UK Renal Registry servers in Bristol. The data collection tools (fields, format etc) are defined by the UK Renal Registry dataset and individual centres specific data formats are converted appropriately. There are no standardised data collection instruments at individual sites.

### ***WP3:9.2 Data handling and record keeping***

UK Renal Registry data will be imported into the statistical package R, for subsequent reshaping, assessment of missingness, summary statistics and fitting of relevant models which will inform the health economic model. The health economic model will also be run in this environment. WP3 intends to develop analysis scripts that take the raw UK Renal Registry data and produce the relevant results without intermediate files.

### ***WP3:9.3 Access to data***

Data will be securely transferred between the UK Renal Registry, Keele and the University of Sheffield. On arrival to the University of Sheffield this anonymised data will be transferred to secure servers with user privileges limiting its access to the immediate study team.

## **WORK PACKAGE 4 (WP4): SYNTHESIS OF QUALITATIVE AND QUANTITATIVE DATA**

### ***WP4: Overview***

No new data will be collected for WP4. Analysis will combine the data from previous work packages to synthesise and interpret it in order to develop a number of *potential* intervention bundles that could possibly reduce or eliminate the centre effect in home therapy uptake. The impact of these bundles, or bundle components will then, in an iterative process with the data from WP2 and WP3, be assessed using the explanatory statistical model and the updated health economic model in terms of the trade-off between their benefits and ceiling costs.

#### **WP4: Design and theoretical frameworks**

Evidence review has highlighted the absence of attempts to integrate data from different components of mixed methods studies [69a]. Our study methods seek to overcome these shortcomings by undertaking a synthesis guided by two complementary frameworks. These frameworks will determine how data from the ethnography, quantitative work and health economics components are described and combined. Most importantly, these frameworks provide a clear structure to guide the synthesis and integration of research findings derived from multiple sources and using multiple methods. First, the factors affecting the uptake of home therapies (WP1 and WP2) will have been mapped onto each domain of the NASSS framework [4] during the course of the study to date (stage 1) (see Table 1).

The evidence for the importance and significance of each factor, its mechanism of action, complexity within each of the seven NASS framework domains and scope for change over time will be discussed in a team workshop (stage 2) which will also look for patterns and themes in the data from different sources. Synthesis will take place iteratively, with opportunities for re-analysis and further exploration of data from WP1-3 following the first team workshop, so that further quantitative analysis of national survey data, qualitative re-analysis of the ethnographic data and generation of associated costs from the health economic model can contribute to the synthesis (stage 3).

After the second round of synthesis, a second team workshop will review the additional analyses and finalise the list of factors affecting home dialysis uptake; identify factors which are co-dependent; use the effect estimates from WP3 to assess the relative impact of each factor on home dialysis uptake, time on home therapy, QALY gains and costs (stage 4). This process will be supported by the review of existing literature which explores the underlying mechanisms. The first intervention development workshop in WP5 will provide an opportunity for the synthesised results to be discussed and challenged by a wider group of staff and patient stakeholders using the APEASE criteria. Alongside the NASSS framework, synthesis will be guided further by the 8-stage process of intervention development outlined by the authors of the COM-B framework.[5] This process will bridge across between WP4 and WP5 so that the intervention development work in WP5 draws on the synthesis undertaken in WP4 and is directly informed by it (see Table 1). The COM-B will also prompt policy-level components of the interventions to be identified.

**Table 1: Use of the NASSS framework to guide data synthesis in WP4**

Domain	Sub-domain	WP4 Stage 1	WP4 Stage 2	WP4 Stage 3	WP4 Stage 4
Condition (ESRD)	- Nature of condition - Socio-cultural influences	Mapping of findings from WP1 (ethnography), WP2 (quantitative analysis) onto each domain of the NASSS framework to identify potentially modifiable factors affecting home therapy uptake	Research team and stakeholder discussion workshop to refine mapping and identify where further exploration of the data is required.  Early identification of mid-range theories	Further quantitative analysis of survey and renal registry data, health economic model and qualitative data from ethnography.  Review of literature surrounding early theory within and beyond specific context	Second team workshop to review the additional analyses and supporting evidence, finalise the list of potentially modifiable factors to be taken forward into intervention development work for WP5
Technology (home therapies)	- Features - Knowledge needed to use				
Value proposition (to patient and provider)	- Supply side value (provider) - Demand side value (patient)				
Adopters (roles, identity, input required)	- Staff - Patients - Carers				
Organisational capacity	- Leadership - Readiness to change - Extent of change required - Work needed to implement change				
Wider system (policy)	- Policy context - Regulatory and legal - Professional - Socio-cultural				
Embedding and adapting over time	- Scope - Organisational resilience				
COM-B Stage 1) Define problem in behavioural terms			2) Select the target behaviour to modify		

## **WORK PACKAGE 5 (WP5): INTERVENTION DEVELOPMENT**

### ***WP5: Overview***

Consultation with clinical staff and evidence from the literature suggest that a complex intervention will be required (referred to from here as a bundle of interventions), which is comprised of individual elements that act on individual modifiable factors. These modifiable factors are likely to be related to: a) patient-clinician interaction; b) renal unit organisation; and c) the wider policy/system context. In developing the bundle of interventions, we will be guided by the Medical Research Council's internationally recognised principles for developing complex health-related interventions.[6] Broadly, the intervention will be developed and tested with patients and health-care providers to ensure feasibility and acceptability, again working iteratively with the health economics team to ensure cost effectiveness. It is expected that the intervention bundle will comprise a range of components that will have relevance for all stake-holder groups including commissioners, provider units, recipients of dialysis treatment and their care-givers. Potential examples would include commissioning guidance, role and size of financial incentives, recognition of bias, need for greater support for certain groups of patients and caregivers, awareness of opportunities and innovative approaches to overcoming barriers.

## **WP5:7 STUDY PROCEDURES**

### ***Co-design with Reference Group***

A co-design approach will be used to develop the intervention over a 6-month period, with patients and clinicians working in an equal partnership with the research team. We will do this by convening an independent Reference Group (RG) of renal clinicians and renal patients that will work with us through three interactive workshops. Membership of the RG will consist of: 4 doctors (consultants, registrars), 4 nurses (home therapy specialist nurses, dialysis nurses, ward nurses), three allied health professionals (dietitian, psychologist/counsellor, social worker); 6 patients (two pre-dialysis, one PD, one home haemodialysis, two in-centre haemodialysis, who will all be members of the national clinical study group for dialysis run by Kidney Research UK); and two policy leads (one national lead, one regional commissioner). Members will be identified through the existing extensive networks of the project team and the advisory group. They will be drawn from across England and will not have had any direct involvement in WP1. The RG will take part in two interactive workshops (one initial full-day workshop, followed by one half-day workshop).

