**5:WP2:** The survey will be sent to all 52 of the Dialysis Units in England. The survey data will be linked with the patient level routine data returns made from the 52 units to the UK Renal Registry. Linkage will be undertaken at Keele University.

**5:WP3:** Is all data driven. Research data will be obtained through Keele University and the UK Renal Registry under a data-sharing agreement.

**5:WP4:** The data synthesis, using aggregated data, will be undertaken by the research team in workshops held on University premises.

**5:WP5:** The intervention development will be co-designed with an Independent Reference group comprising patients, carers, health professionals and members of the national dialysis reference group. These workshops will be held on University Premises.

***In the following sections the protocol is ordered by WORK PACKAGE. Each paragraph is numbered first by the WP identifier, e.g. WP1: detail on rationale and design where needed, followed by the main section number and the appropriate subsection where relevant in the following order:***

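### The WP5 Reference Group is said to include carers, but its fixed list of 19 members has no carer place, so direct carer input to choosing the intervention is not secured

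*Protocol*

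**What the plan says.** Two current parts of the protocol describe the same group.

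- **Section 5 (Study Setting, WP5 entry):** the intervention is to be co-designed with an "Independent Reference group comprising patients, carers, health professionals and members of the national dialysis reference group".
- **WP5:7 (Co-design with Reference Group):** the team plans on "convening an independent Reference Group (RG) of renal clinicians and renal patients". A numbered list by role follows, and its patient entry reads "6 patients (two pre-dialysis, one PD, one home haemodialysis, two in-centre haemodialysis, who will all be members of the national clinical study group" for dialysis. Members are found through the networks of the project team and the advisory group, come from across England, and must not have been directly involved in WP1.

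Three other parts bear on the point.

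- **WP5: Overview** expects the bundle's components to have "relevance for all stake-holder groups including commissioners, provider units, recipients of dialysis treatment and their care-givers".
- **WP5:7.1 and WP5:7.2** give the group its task. Workshop 1 reduces 6-10 modifiable factors to 3-5 by consensus and produces 3-5 candidate bundles. Workshop 2 refines these to 2-3. The experience that Workshop 1 draws on is that of patients and clinicians.
- **Section 11.3** describes a separate Patient Advisory Group of present or past dialysis users who will contribute to the WP5 workshops. It treats this as essential to a final intervention that is acceptable and relevant to patients, care-givers and families.

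**The concern.** A team that recruits to the WP5:7 list will not convene the group that section 5 describes. The list gives a number for each role and is not offered as a set of examples, so a carer place cannot be read into it.

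Carers are not peripheral to this intervention. The protocol's definitions say that home haemodialysis is often done with family support. The theoretical framework says that home therapy asks for new behaviour from carers and family as well as from patients and staff. The WP1 rationale counts family and carers among the key stakeholders. Factors that turn on the burden or willingness of carers could therefore be kept or dropped at the short-listing step with no carer present, while section 11.3 claims acceptability to carers for the result.

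**Working it through.** **1. Add up the listed places (WP5:7).**

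| Role | Places |
|---|---|
| Doctors | 4 |
| Nurses | 4 |
| Allied health professionals | 3 |
| Patients | 6 |
| Policy leads | 2 |
| Carers | none listed |

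- Patients by treatment: 2 pre-dialysis + 1 PD + 1 home haemodialysis + 2 in-centre = 6, which agrees with the stated 6.
- Clinicians: 4 + 4 + 3 = 11.
- Whole group: 11 + 6 + 2 = 19. The protocol states no total to compare with this.
- Carers: 0 of 19.

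**2. Set the two descriptions side by side.**

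| Constituency in section 5 | In the WP5:7 list? |
|---|---|
| Patients | Yes, 6 |
| Carers | No |
| Health professionals | Yes, 11 |
| Members of the national dialysis reference group | Unclear: a national clinical study group appears only as the source of the six patients |

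The second row is a plain contradiction. Both texts are current, and the protocol has no rule on which section prevails.

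**3. Look for another route by which a carer could take part in WP5.**

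- *Patient Advisory Group (section 11.3).* It contributes to the workshops, but its membership is defined by use of dialysis.
- *Inter-CEPt Advisory Group (section 11.3).* It has independent patient representation; carers are not mentioned.
- *PPIE expert group (sections 10.2 and 11.3).* It meets at month 25 to inform the overview of the intervention; the protocol does not say that it includes carers.
- *Carers interviewed in WP1 (WP1:7.1).* There are 5 per site at 4 sites, so 5 × 4 = 20. WP5:7 bars from the Reference Group anyone directly involved in WP1, so these 20 cannot sit on it. Their evidence passes through the WP4 synthesis, where carers are a named sub-domain under adopters in Table 1.

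No route guarantees a carer in the room. The indirect route, from WP1 interviews through the synthesis to the factors shown at Workshop 1, does exist.

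**4. Compare what is claimed with who decides.** Objective 4 (section 3) and the testing described in WP5: Overview name only patients and professionals. The claim that extends to care-givers and families is in section 11.3, and the group it rests on there is one of dialysis users.

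**The case against.** The strongest reply is that carers are not ignored. The Reference Group starts from 6-10 factors synthesised from WP1 to WP3, and that evidence includes 20 carer interviews. The Patient Advisory Group adds patient voices to the workshops beyond the six seats, and the advisory and PPIE expert groups meet on the overview of the intervention at months 24 and 25. Objective 4 promises acceptability to patients and professionals only, and the WP5 overview speaks of relevance to care-givers, which is less than tested acceptability. All of this stands, and it limits the consequence. It does not remove the contradiction between section 5 and WP5:7, and it puts no carer into the consensus step.

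A reader might go further and infer that the bundle cannot be tested for acceptability to carers or to under-served patients. The documents do not support that.

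- For carers, the indirect evidence route is real, so the accurate statement is that direct input is not secured.
- For BME and more deprived patients, WP5:7 sets no ethnicity or deprivation criterion and takes all six patients from one national group, but nothing in it excludes such patients. About half of the WP1 semi-structured interviews are planned with BME and socioeconomically deprived patients (WP1:7.0.5), and this evidence also reaches WP5 through the synthesis.
- The protocol does not describe the make-up of the national study group, and members are identified through networks and not drawn at random. A calculated chance that the six would include no BME patient would therefore rest on assumptions that the documents cannot back.

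**Conclusion.** The contradiction on carers holds. Section 5 says they are in the Reference Group; the WP5:7 list gives them 0 of 19 places, and no other group described for WP5 is defined to include them. Direct carer input to the step that cuts 6-10 factors to 3-5 and shapes the bundles is therefore not secured, although section 11.3 claims acceptability to care-givers and families. Carers' views reach WP5 only second-hand, from the 20 WP1 interviews and the synthesis.

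This rests on two readings: that the WP5:7 list is complete, which its wording and fixed numbers support, and that the Patient Advisory Group is limited to dialysis users, as section 11.3 defines it. A listed patient might happen also to be a carer, but the plan does not ask for that.

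The absence of any statement on how BME and more deprived patients will be found for the six patient seats is a lesser matter. It is worth a sentence in the protocol, given that inequity is part of the study's stated problem, but it is not an error in the plan.

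**What to change.** - **WP5:7:** amend the membership list to match section 5 by adding carer places. Two would be a reasonable example, either as extra seats (19 + 2 = 21) or by reallocating two existing seats to stay at 19. Amend the opening description of the group, which names only clinicians and patients, in the same way.
- **WP5:7.1:** include carers among those whose lived experience informs the discussion of candidate bundles.
- **Section 11.3:** tie the claim of acceptability to care-givers and families to the group that will contain carers.
- **Secondary suggestion, WP5:7:** add a sentence on how BME and more deprived patients will be sought among the six patient members. A fixed quota is not needed.

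The cost is protocol wording and a few more attendees to recruit and brief; WP5:7.1 already provides an optional pre-workshop session. If seats are reallocated, some professional input is given up. The change should be made before the Reference Group is recruited, because carers cannot co-design a bundle that has already been chosen.
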